8. *Objectives*

The objective of this research study is to better understand patterns of recovery after total hip arthroplasty (THA) and total knee arthroplasty (TKA). The study will evaluate how pain, pupil diameter as a measure of LC activity and cognitive (i.e., thinking style) determine patterns of recovery, and the study will evaluate the efficacy of gabapentin versus placebo for improving recovery after surgery.

Research hypothesis: The null hypothesis (H_0) is that modeled trajectory of change in pain intensity report after THA and TKA does not differ between oral gabapentin and placebo in a manner dependent on its interaction with preferred cognitive style and pre-surgery pupil resting diameter. The alternative hypothesis (H_1) is that there is a difference between the two groups which is dependent on these interactions. The null hypothesis will be tested through contrasting the fit of a null model (m_0), with only change parameters and prognostic covariates, and the full model (m_1), which includes all of the predictors in null model with the addition of randomized treatment group, cognitive style, resting pupil diameter, and all two and three-way interactions. The difference in fit will be evaluated using a likelihood ratio test, as further described below.

$$H_0: -2 * (\loglik[m_0] - \loglik[m_1]) = 0$$

$$H_1: -2 * (\loglik[m_0] - \loglik[m_1]) > 0$$

Study objective: The primary objective is to determine the effectiveness of oral gabapentin to speed recovery from pain, as measured by growth curve modeling, after THA or TKA and how this effectiveness is modified by preferred cognitive style and pre-surgery resting pupil diameter.

Secondary objectives are planned to explore the role of these factors interact to predict other outcomes from surgery, including speed of gain in activity, assessed by actigraphy, speed recovery from self-assessed disability, and time to cessation of opioid use; to explore whether change in pupil diameter to acute experimental pain explains additional variance in a 4-way interaction compared to the 3-way interaction in the primary analysis.

Section 3: Trial Methods

9. Trial design

[figure not shown]
The trial is a two-center, randomized, double-blinded, parallel-group, placebo-controlled trial. Treatment allocation is a 1:1 ratio. Patients are randomized to either gabapentin or placebo control.

10. Randomization

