Study period	Screen	Baseline	In hospital	Daily diaries	Follow up 1	Follow up 2	Phone	Orthopaedic clinic visits
Visit number	0	Visit 1			Visit 2	Visit 3		
Week		-4 to -2*	0-3 days	0-8	8	26	12,16,20,52	2, 6, 12-16, 26, 52
Informed consent		X						
Demographic		X						
Medical/surgical history		X						
Questionnaires		X			X	X		
Pain testing & pupillometry		X						
Randomisation		X						
Study drug dispensing		X						
In hospital pain/medication data & disposition			X					
Daily diary & accelerometry		X		X				
Phone assessment of pain, medication use, function							X	
Joint function								X

*Study medication begins at -2 weeks and continues until 3 weeks after surgery

Final analysis of the gabapentin vs placebo comparison with and without inclusion of interactions with preferred cognitive style and pre-surgery pupil responses to pain will take place when all patients have completed the 12-month follow-up and data for the primary endpoint have been cleaned, which occurred in May 2022. Results were anticipated to be posted by Jan, 2023, but complexities associated with generation of a novel psychologic construct from the final dataset and defining parameters for pupil assessment prevented completion of the primary analysis until Mar, 2023.

15. *Timing of outcome assessments*

The schedule of study procedures is provided in the protocol and summarized in the table below.

Section 4: Statistical Principles

16. *Level of statistical significance*

All applicable statistical tests will be 2-sided and will be performed using a 5% significance level.

17. *Adjusting for multiplicity*

The primary analysis involves a single model-based inference that will be interpreted at the 5% threshold of statistical significance. If the primary analysis is significant, each main factor, all two way interactions, and the three way interactions will be evaluated and each will be interpreted at the 5% level of significance with no adjustments made for multiplicity.

18. *Confidence intervals*

All confidence intervals presented will be 95% and two-sided.

19a. *Definition of adherence to the intervention and how it is assessed*

Compliance is assessed based on the number of daily diary entries after hospital discharge. It is defined as:

$$\% \text{ compliance} = (\text{number of entries}/\text{number of days entries were to be completed}) * 100\%$$

19b. *How adherence will be presented*

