This will be presented in CONSORT diagram format rather than as a table, with numbers and reasons for withdrawal and/or exclusion from analysis given at each stage

24c. *Reasons for withdrawal/lost to follow up data*

The numbers (with reasons, if available) of losses to follow-up (drop-outs and withdrawals) over the course of the trial will be summarized by treatment arm.

25a. *List of baseline characteristics to be summarized*

Patients will be described with respect to age, sex, race, ethnicity, medications, number of painful conditions excepting the hip and their locations, cognitive – optimism cognitive construct generated from questionnaires, baseline pain from the daily diaries prior to surgery, and surgical approach (anterior vs posterior).

25b. *How baseline characteristics will be described*

Categorical data will be summarized by numbers and percentages. Continuous data will be summarized by mean, SD and range if data are normal and median, IQR and range if data are skewed. Minimum and maximum values will also be presented for continuous data. Tests of statistical significance will not be undertaken for baseline characteristics; rather the clinical importance of any imbalance will be noted.

Section 6: Analysis

26. *Outcomes and timings*

Primary outcome: Worst pain intensity measured using a 0 to 10 numerical rating scale on a daily diary. Measurements will be obtained each evening from day 0 (surgery) to day 56 after surgery. The pain measurements will be evaluated in a statistical model using an intercept (i.e., immediate pain after surgery) and slope (i.e., rate of change of pain during the observation period).

Secondary outcomes: Daily measurements such as physical activity, as measured via actigraphy, disability, as measured by daily diaries and weekly WHODAS 2.0 scores, and opioid self-administration, as measured by daily diaries will be collected from day 0 (surgery) to day 56 after surgery. Questionnaire and cognitive game data will be assessed at baseline and follow-up. Validated scoring systems from the individual items will be used to score each questionnaire or measure. These outcomes will not be used in the primary analysis.

27a. *Analysis methods to be used and*

27b. *Adjustments for covariates*

Primary analysis:

Overview

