The primary analysis will model trajectory of recovery of daily worst pain ratings and examine several sources of influence on this recovery. Sometimes referred to as mixed-effects models, or hierarchical linear models, growth curve modeling allows specification of a change trajectory that is unique to each individual. The nature of the common form of changes in daily pain will be modeled using a curvilinear form (e.g., polynomial regression). Through the use of fixed and random effects, variations in intercepts (i.e., levels of pain on day of discharge) and slopes (i.e., change in daily pain over time) can be examined using the pre-specified influences outlined below. To model individual pain trajectories, several model form candidates will be examined with the best fit determined using a Bayesian Information Criterion. These model forms will include linear, quadratic, cubic, and log(time), and each of these model candidates will be employed that reflect a fundamental change in trajectory that occurs during the observation period. Based on preliminary data it is highly likely that a log(time) form will be chosen.^{1,2}

To examine the proposed hypotheses, several key sets of predictors will be specified including patient characteristics, operative characteristics, cognitive style, randomized treatment assignment, and pre-operative pupil diameter response. Each of these predictors are described below:

Patient characteristics: To adjust the associations for individual age and sex will be entered into the model.

Operative characteristics: To adjust the associations for any subtle differences in medical care, study site, and surgery type (hip or knee arthroplasty) will be entered into the model.

Cognitive style: Multidimensional scaling of the pre-operative questionnaires will be conducted to create a unidimensional scale that represents a broader spectrum of cognitive style that ranges from optimism/acceptance of pain to catastrophizing. This novel predictor will be examined for reliability and correlations with the original scales. If insufficient reliability ($\alpha < 0.70$) or construct validity ($r < |0.40|$) with the original scales cannot be obtained, the analysis will proceed using the originally scaled catastrophizing predictor.

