Pupil diameter: Pupil recordings will be conditioned to remove artifacts (e.g., blinks), saccades, and deviations from central gaze that might bias recordings. A response window with appropriate lag reflecting delayed onset of pupil response due to physiological delays will be used to define change in diameter to each stimulus as previously reported.¹⁷ Two pupil measurements will be estimated from the session data, the mean pupil diameter during baseline (i.e., pre-stimulus) and the modeled response to pupil to 50-degree stimulus.

Gabapentin: Randomized treatment assignment of either gabapentin or placebo will be a fundamental predictor of trajectory.

These individual predictors sets will then be used to test the primary hypothesis that gabapentin alters time course of recovery after arthroplasty in a manner dependent on its interaction with preferred cognitive style and pre-surgery pupil diameter. The primary statistical inference will be the difference in the likelihood ratio between two nested models using a chi-square test with K degrees of freedom (i.e., K being the difference in the number of parameters between the two models). The first model (i.e., null model) will consist of the pain trajectory model with the addition of patient characteristics and operative characteristics. The second nested model will add medication assignment (gabapentin versus placebo), cognitive style (catastrophizing \leftrightarrow optimism latent score), and resting pupil diameter, and all two-way interactions and three-way interaction between these 3 predictors (i.e., 3 two-way, and 1 three-way interaction for both intercept and slope parameters) from the first nested model. This approach allows a single likelihood ratio test of the primary hypothesis and will be interpreted using a two-tailed hypothesis test using $p < 0.05$. A statistically significant difference in the likelihood ratio test will be interpreted as evidence to support the primary hypothesis in that the interaction of these predictors impacts some aspect of the change process beyond that of the basic model. We have planned several sensitivity analyses using multiple imputation to account for missing data.

Several exploratory secondary analyses of the data set:

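### No planned model lets the gabapentin effect change when study drug stops at week 3, so a treatment-by-slope term over days 0–56 could be misread as slower recovery

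*SAP*

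**What the plan says.** - **Treatment period** (Section 14, Table 1 footnote): "Study medication begins at -2 weeks and continues until 3 weeks after surgery".
- **Observation window** (Section 26): "Measurements will be obtained each evening from day 0 (surgery) to day 56 after surgery".
- **Outcome parameters** (Section 26): an "intercept (i.e., immediate pain after surgery) and slope (i.e., rate of change of pain during the observation period".
- **Time forms** (Section 27a/27b, Overview): "These model forms will include linear, quadratic, cubic, and log(time"), chosen by BIC. The SAP adds: "Based on preliminary data it is highly likely that a log(time) form will be chosen". It also says that candidates will "reflect a fundamental change in trajectory that occurs during the observation period", but gives no time for such a change and no link to the end of study drug.
- **Where treatment enters** (Section 27a/27b): treatment, cognitive style and resting pupil diameter are added with "3 two-way, and 1 three-way interaction for both intercept and slope parameters". That is 7 terms on each parameter, so 7 × 2 = 14 for a one-slope form.
- **Inference**: one likelihood ratio test at 5%. If it is significant, Section 17 has the main factors and interactions each read at 5% without adjustment.
- **Target** (Section 8): "The primary objective is to determine the effectiveness of oral gabapentin to speed recovery from pain, as measured by growth curve modeling".
- **Sensitivity analyses** (Section 27e): multiple imputation, baseline values of the outcomes, diary data out to 12 months, and race and surgeon. None concerns the end of study drug, and the third adds more off-drug data.

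**The concern.** Patients are already on study drug at day 0, so relief present while on drug goes mainly into the intercept. If that relief is lost when the drug stops, the arms converge after day 21. A single smooth slope can describe this only as a slower fall in pain under gabapentin. The planned slope term therefore mixes two things: a change in how fast patients recover, and the loss of an effect that existed only while the drug was taken.

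The objective is about speed of recovery, and single terms will be read one at a time after a significant omnibus test. A positive treatment-by-slope term could then be misread as gabapentin slowing recovery when it had lowered pain on every on-drug day and harmed on none. The slope interactions with style and pupil diameter are open to the same ambiguity, though its size there has not been calculated.

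**Working it through.** **What can be reproduced.** The SAP states N = 250 and power above 90% from a simulation, but gives no effect sizes or variances, so that figure cannot be rebuilt. The point does not depend on it.

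**Inputs from the SAP.** 57 daily ratings (days 0–56): 22 up to day 21 (22/57 = 38.6%) and 35 after it (61.4%). Allocation is 1:1, so 125 per arm.

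**Assumption.** The true arm difference δ (gabapentin minus placebo) is −1 on days 0–21 and 0 on days 22–56.

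**Formula.** With complete balanced data, the treatment contrast in a random intercept-and-slope model is the least-squares projection of δ on the time form x:
- slope = Σ(x − x̄)δ / Σ(x − x̄)²
- intercept = mean(δ) − slope × x̄

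**Log form, x = ln(day + 1).** x̄ = 3.095; the mean of x over days 0–21 is 2.203; Σ(x − x̄)² = 45.12.
- slope = 22 × (3.095 − 2.203) / 45.12 = 19.61 / 45.12 = **+0.43 per log-day**
- intercept = −22/57 − 0.4346 × 3.095 = −0.386 − 1.345 = **−1.73** (truth −1.0)
- fitted at day 21: −1.731 + 0.4346 × ln 22 = **−0.39** (truth −1.0)
- fitted at day 56: −1.731 + 0.4346 × ln 57 = +0.03 (truth 0)

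Using ln(day) from day 1 gives a slope of +0.44, so the offset does not matter.

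**Linear form.** slope = 22 × (28 − 10.5) / 15,428 = 385 / 15,428 = +0.025 per day; intercept = −0.386 − 0.025 × 28 = −1.08; fitted at day 56 = +0.31.

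**Polynomials, same δ.** Quadratic: initial slope +0.053 per day. Cubic: initial slope −0.009 per day, with a fitted −0.55 at day 21. Neither has a break there.

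**Other assumed profiles (slope difference).**

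| Profile | log | linear, per day |
|---|---|---|
| −1 to day 21, fading over 7 days | +0.43 | +0.026 |
| Builds linearly to −1 at day 21, then lost | +0.11 | +0.010 |
| Builds to −1 by day 7, held to day 21, then lost | +0.24 | +0.018 |
| Constant −1 throughout | 0 | 0 |
| Builds to −1 at day 21, persists | −0.33 | −0.015 |

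The slope is positive when relief ends with the drug, and not when it persists.

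**How often the slope term would be significant.** SE = √[2(τ² + σ²/45.12)/125], where τ is the SD of individual log-slopes and σ the residual SD, both assumed. With τ = 0.6 and σ = 1.5: √[2(0.36 + 0.0499)/125] = 0.081, so z = 0.4346/0.081 = 5.4. With σ = 1.5 throughout, the chance of a significant positive slope is:

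| On-drug relief | τ = 0.5 | τ = 0.7 | τ = 1.0 |
|---|---|---|---|
| 0.25 point | 35% | 21% | 13% |
| 0.5 point | 88% | 65% | 39% |
| 1.0 point | >99% | >99% | 92% |

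These are for a two-arm slope comparison alone, not for that term inside the interaction model after the omnibus test.

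**With a change at day 21.** Adding an off-drug step to the log form gives intercept −1.00, slope 0.00 and step +1.00, which recovers the assumed truth.

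**The case against.** The strongest reply is that the SAP never commits to the misreading. A reader might infer that the plan will report an effective analgesic as slowing recovery, or that the primary test is unsound. The documents support neither.

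- The primary inference is one omnibus test over intercept and slope terms together. It has no direction, and transient relief would rightly count as an effect on the trajectory. This stands.
- Section 8 speaks of speed as measured by growth curve modelling and does not equate speed with the slope coefficient. Section 17 gives no rule for reading a slope. This stands, but the absence of a rule is what leaves the term open to misreading.
- Under the log form the fitted curves do not show harm. Gabapentin is below placebo through day 52 and at most 0.03 points above it after that; the mean fitted difference is −0.77 on days 0–21 and −0.14 on days 22–56. Read jointly, the terms say lower early pain, then convergence. This stands; the 0.31-point excess at day 56 belongs to the linear form, which the SAP does not expect.
- BIC may choose another form, and the phrase about a fundamental change leaves some room. This stands in part: the cubic has no reversed initial slope. But no listed form breaks at week 3, and nothing says the treatment contrast may change there.
- Section 7 offers a mechanism by which gabapentin could alter recovery itself. Following patients beyond the end of drug is a coherent design, and the 61% off-drug share is not an error.

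**Conclusion.** The point holds as a gap in interpretation and supportive analysis. No planned model allows the treatment effect to change when study drug stops. Under the expected one-slope form, relief confined to the on-drug period therefore appears as an exaggerated intercept and a positive slope term: −1.73 and +0.43 per log-day for an assumed 1-point effect, with relief at day 21 understated at −0.39 against −1.0. The slope term alone cannot tell slower recovery from loss of on-drug effect.

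This is conditional on relief ending with the drug. The sign was the same for every such profile tried with the log and linear forms, but the sizes and the chance of significance rest on assumed effects and SDs that the SAP does not give. The omnibus test remains valid. The change is inexpensive and worth making, but the plan does not fail without it.

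**What to change.** Keep the primary test and the dosing schedule as they are.

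1. In Section 27a/27b, state that the gabapentin intercept and slope terms, and their interactions, are interpreted jointly, and that a slope term alone will not be described as speed of recovery.
2. Add one supportive model in which the treatment effect and its style and pupil interactions may change, in level and slope, at the scheduled end of study drug (day 21). Label it by the date it was specified: Section 14 places completion of the primary analysis in March 2023, so it should not be called pre-specified if added later.
3. Report fitted arm differences averaged over days 0–21 and over days 22–56.
4. Judge speed from the slope contrasts within each period. A difference that merely persists after day 21 is not evidence of speed, since constant relief has a slope contrast of 0.

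The cost is SAP wording and one extra model on diary data already collected. The downside is a few more estimates and a more qualified reading of the slope.

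### The primary likelihood ratio test uses a plain chi-square reference; with about 250 patients and 14 tested parameters its true size is about 6.5%, not 5%

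*SAP*

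**What the plan says.** SAP items 27a/27b compare a null growth model with a full model: "The primary statistical inference will be the difference in the likelihood ratio between two nested models using a chi-square test". The degrees of freedom, K, are the difference in parameter count. The full model adds three main effects and "3 two-way, and 1 three-way interaction for both intercept and slope parameters".

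The null model carries the trajectory plus covariates: "individual age and sex will be entered into the model", and likewise "study site, and surgery type (hip or knee arthroplasty) will be entered into the model".

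BIC picks the time form from linear, quadratic, cubic and log(time), with a clear expectation: "Based on preliminary data it is highly likely that a log(time) form will be chosen".

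Item 16 sets the level: "All applicable statistical tests will be 2-sided and will be performed using a 5% significance level". Item 17 treats the primary comparison as a single inference. If it is significant, it opens tests of every main effect and interaction, each at 5% without adjustment. Item 11 gives a sample size of 250.

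The SAP does not give a numerical value for K. It also does not say whether the models are fitted by maximum likelihood, list which trajectory coefficients are random, or name any small-sample correction.

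**The concern.** The chi-square reference for a likelihood ratio statistic is a large-sample approximation. Its accuracy depends on how many independent units inform the tested parameters relative to how many parameters are fitted. Each patient may supply up to 57 diary entries (day 0 to day 56), so the data set looks very large. Every tested predictor, however, is fixed within a patient, so the relevant sample is the number of patients. With 14 or more parameters tested at once on about 250 patients, the statistic is on average somewhat larger than its chi-square reference, and the test rejects too often under the null.

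The trial's only confirmatory test is affected. Any excess error there also passes to the unadjusted follow-up tests in item 17. Item 27 reuses the method for the secondary trajectories and for the four-way interaction.

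**Working it through.** **No figure of the plan to reproduce.** The SAP states no type I error beyond the nominal 5%. The power in item 11 (above 90% at 250) came from simulations whose effects and variances are not given, so it cannot be rebuilt. Power of 90% on 14 df would need a noncentrality of 23.0.

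**Inputs from the SAP**
- N = 250 (item 11).
- q = 7 tested terms per trajectory coefficient: 3 main effects + 3 two-way + 1 three-way (items 27a/27b).
- c = 5 null-model columns: constant, age, sex, site (two centres, so one column) and surgery type.
- p = trajectory coefficients: 2 for linear or log(time), 3 for quadratic, 4 for cubic. K = p × q = 14, 21 or 28.

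**Assumptions, not fixed by the SAP**
- Maximum likelihood fitting.
- Every trajectory coefficient random.
- Covariates and tested terms acting on each coefficient.
- Balanced diaries (relaxed below).

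**Exact calculation, 14 df.** Under these assumptions the likelihood ratio statistic equals −N ln Λ, where Λ is Wilks' lambda with 7 hypothesis df and 250 − 5 − 7 = 238 error df.
1. The plain chi-square critical value on 14 df is 23.68.
2. Λ at that point = exp(−23.68/250) = 0.9096, and √Λ = 0.95373.
3. For p = 2 the exact F is [(1 − √Λ)/√Λ] × (238 − 1)/7 = (0.04627/0.95373) × 237/7 = 1.642, on 14 and 474 df.
4. P(F > 1.642) = 0.0647. The true size is about 6.5%.

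**Bartlett approximation, any p.** The multiplier is m/N with m = N − c − q − (p − q + 1)/2. For p = 2, m = 238 + 2 = 240. Then 23.68 × 240/250 = 22.74, and P(χ² on 14 df > 22.74) = 0.0647, which agrees with the exact result.

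| Form (all coefficients random, N = 250) | df | m | True size | Corrected critical value |
|---|---|---|---|---|
| Linear or log(time) | 14 | 240 | 6.5% | 24.67 (plain 23.68) |
| Quadratic | 21 | 239.5 | 6.9% | 34.10 (plain 32.67) |
| Cubic | 28 | 239 | 7.3% | 43.24 (plain 41.34) |

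Monte Carlo draws of Λ agree with these sizes to within 0.1 percentage point. With the Bartlett multiplier applied, size returns to about 5.0% in all three rows.

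**Affected band at 14 df.** The corrected critical value of 24.67 has a plain chi-square p of 0.038. The band is therefore about 0.038 to 0.05.

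**Fewer random terms, N = 250**
- Random intercept only: 5.7% (14 df) and 5.5% (28 df).
- Cubic mean with only intercept and linear slope random: 6.0% (28 df).

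**Fewer patients analysed (14 df, random intercept and slope).** Item 20 restricts the analysis set to patients who received drug and gave at least one later pain score. The resulting number is not stated. Size is 6.7% at 220, 6.9% at 200 and 7.1% at 180.

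**Unbalanced diaries.** Direct simulation of a random intercept plus log(time) slope model, fitted by maximum likelihood with about 20% skipped diaries and 25% early dropout, gave 6.4% (6,557 runs, standard error 0.3). The result does not depend on complete diaries.

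**The case against.** The strongest reply is that nothing is misstated. A chi-square likelihood ratio test of nested mixed models is the ordinary default with about 250 subjects. The 5% in item 16 is a nominal level, and about 1.5 percentage points of excess is small. That stands as a limit on severity. It does not remove the discrepancy: the size can be calculated, it is above 5% in every structure examined, and it arises even when the model is correct.

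A second reply is that the figures rest on a random-effects structure the SAP leaves open. That also stands, and it is why a range is given. Item 27 does describe individual variation in both intercepts and slopes, so random intercept plus slope is the natural reading.

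A reader might go further and infer that the test runs near one and a half times its stated level. That needs BIC to select a cubic and all four of its coefficients to be random. The SAP commits to neither and expects log(time). Nor is 7.3% a ceiling, because it would rise with fewer patients. A reader might also infer that any result in the affected band is a false positive. It would only be a result that misses a true 5% threshold.

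**Conclusion.** The point holds as a minor calibration defect in the single confirmatory test. Under the expected log(time) form the size is about 6.5%, roughly 30% above nominal (6.5/5 = 1.3). This assumes maximum likelihood, 250 patients, random intercept and slope, and the SAP's four covariates on each trajectory coefficient. Across plausible structures at 250 patients the range is about 5.5% to 7.3%. Only the test's reference distribution is affected, not the fitted estimates, and the practical consequence is confined to a primary p-value just under 0.05.

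**What to change.** In items 27a/27b, state that both models are fitted by maximum likelihood and that the likelihood ratio statistic is referred to a parametric-bootstrap null distribution (or a Bartlett-corrected chi-square) instead of the plain chi-square. In the same place, state which trajectory coefficients are random and the value of K under each candidate time form, since the correction depends on both. Apply the same rule to the four-way interaction test and to the secondary trajectory tests that reuse the method.

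The cost is a sentence or two, some computing time for the bootstrap, and a slightly larger primary p-value. The corresponding small loss of power should be accepted knowingly.
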